2.3 Sample Size and Power

Seqirus QIVc will be tested against comparator, i.e. US-licensed comparator QIV. The treatment randomization ratio is 2:1 (Seqirus QIVc: Comparator QIV).

This study is designed to achieve at least 90% power to demonstrate noninferiority for all of the 8 endpoints: seroconversion rates for 4 strains and Geometric Mean Titers (GMTs) for 4 strains using a one-sided alpha of 0.025 for each comparison. No alpha adjustment for multiple endpoints will be made. For comparisons of Seroconversion rate (SCR) a noninferiority margin of 10% (Comparator QIV-Seqirus QIVc) will be employed. It is assumed that the SCRs for A/H1N1, B strains and A/H3N2 based on Cell-based Trivalent Influenza Vaccine (TIVc) are 81%, 69% and 85% respectively. These estimates are based on the estimated SCR rates of historical data, namely from study *V58P16*.

It is also assumed that the expected difference between antibody titers (QIV minus QIVc) is consistent with the SCR differences reported as per *V58P16*, namely 7% for A/H1N1 and 5% for A/H3N2 (based on the MN assay).

It is assumed that there is no difference between Seqirus QIVc and the comparator QIV for the B/strain.

For comparison of GMT ratio, a noninferiority margin of 1.5 (Comparator QIV/ Seqirus QIVc, equivalent to a difference on the log scale of 0.405465108) will be employed for the assessment for the A/H1N1, A/H3N2 and B strains. It is assumed that the GMT ratios for A/H1N1, A/H3N2 and B strains for QIVc are 1.49 for the A/H1N1, 1.00 for the A/H3N2 (based on the MN assay) and 0.84 for the B-strains. These GMT ratio estimates are consistent to those observed from protocol *V58P16*. It is assumed that the standard deviation of $\log_e(\text{titer})$ is 1.3 across all strains.

Under these assumptions and with n evaluable = 1450 in the Seqirus QIVc group and 725 in the Comparator QIV the power for 4 GMT ratio endpoints is 94.90% and the power for 4 SCR endpoints is 99.40%. The overall global power of the 8 endpoints is then $94.9\% \times 99.4\% = 94.33\%$.

This provides a total N evaluable = 2175. Allowing for a 10% drop-out, 2418 subjects will be recruited for immunogenicity assessment. Approximately 84 additional subjects between 24 through 47 months of age will be enrolled to study CMI

Statistical Analysis Plan

Sponsor Name: Seqirus
Sponsor Protocol ID: V130_10

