6.5.1.1 Statistical Hypothesis

The non-inferiority of Seqirus QIVc compared to the US-licensed comparator QIV will be assessed by the 8 co-primary endpoints of GMT and SCR for A/H1N1, A/H3N2 and the B Strains. Definitions for noninferiority based on endpoints measured by HAI are derived from the FDA Guidance on seasonal inactivated influenza vaccines (Guidance for Industry Clinical Data Needed to Support Licensure of Seasonal Inactivated Influenza Vaccines 2007). A modified definition will be applied to assessment of the endpoint based on the MN assay.

The study will be considered successful if all the 8 co-primary endpoints are achieved. Specifically, Seqirus QIVc will be considered to be noninferior to the US-licensed QIV if, for each of the four strains, the following statistical criteria are met:

A/H1N1 and B strains:

- The upper bound of the two-sided 95% CI on the ratio of the HAI GMTs does not exceed 1.5. The HAI GMT ratio will be calculated as $\text{HAI GMT}_{\text{US-licensed QIV}} / \text{HAI GMT}_{\text{Seqirus QIVc}}$
- The upper bound of the two-sided 95% CI on the difference between the HAI SCRs does not exceed 10%. The difference in HAI SCRs will be calculated as $(\text{HAI Seroconversion}_{\text{US-licensed comparator QIV}} - \text{HAI Seroconversion}_{\text{Seqirus QIVc}})$. The 95% CI will be computed based on the binomial distribution.

A/H3N2 strain only:

Statistical Analysis Plan

Sponsor Name: Seqirus
Sponsor Protocol ID: V130_10

- The upper bound of the two-sided 95% CI on the ratio of the MN GMTs does not exceed 1.5. The MN GMT ratio will be calculated as $\text{MN GMT}_{\text{US-licensed QIV}} / \text{MN GMT}_{\text{Seqirus QIVc}}$
- The upper bound of the two-sided 95% CI on the difference between the MN SCRs does not exceed 10%. The difference in MN SCRs will be calculated as $(\text{MN Seroconversion}_{\text{US-licensed comparator QIV}} - \text{MN Seroconversion}_{\text{Seqirus QIVc}})$. The 95% CI will be computed based on the binomial distribution.

In mathematical notation the statistical hypotheses to be tested for the primary noninferiority immunogenicity analysis corresponds to:

- $H_0: R_i > 1.5$, for any strain
- $H_a: R_i \leq 1.5$, for all strain and
- $H_0: D_i > 10$, for any strain
- $H_a: D_i \leq 10$, for all strain

where R_i is any of the 4 strain-specific post immunogenicity dose GMT ratios:

- (US-licensed comparator QIV) / (QIVc) for B/Yamagata strain

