Adjusted Analysis GMT Model: Log-transformed Post-vaccination HAI (or MN) Titer = Vaccine + Age Strata + Gender + Vaccination History [y/n] + Log-transformed Pre-vaccination HAI (or MN) Titer + Site + Age Strata*Vaccine.

For any strain, the interaction term Age Strata*Vaccine will be removed from the fit of the model if it is assessed to be not significant. For all immunogenicity subgroup analysis, the interaction term will be removed in the fit of the model.

The measure of the unadjusted GMT ratio based on post-vaccination GMTs only will also be presented.

Binary data (i.e., percentages of subjects with seroconversion and with titer $\geq 1:40$) will be summarized for each group using unadjusted estimates and will be reported together with two-sided exact 95% CIs. No multiplicity adjustment to the CI levels will be implemented.

If all 8 co-primary endpoints result in a conclusion of non-inferiority, then overall non-inferiority of Seqirus QIVc compared to the US-licensed comparator QIV will be concluded.

Handling of Missing Values for Immunogenicity Data

For immunogenicity data, it may be reasonable to consider missing immunogenicity values as missing completely at random (MCAR), i.e., not informative. Therefore, the immunogenicity and key secondary analyses will comprise a complete case analysis only, without introducing any bias. Imputation methods will not be used.

Sensitivity Analyses for Handling of Missing Immunogenicity Data

To verify the robustness of the primary analysis results, an exploratory analysis may be performed, in which missing titers were imputed using *multiple imputation*. The evaluation of the robustness of the primary analysis results will be based on a pattern mixture model and a 'tipping analyses' approach using multiple imputation methods.

This sensitivity analysis, if conducted, will be based on the per-protocol analysis set and will serve to evaluate the robustness of the non-inferiority conclusions. Appendix C specifies the details of the exploratory sensitivity analysis.

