A SAS macro has been created for doing PMMI as described. This macro allows sampling from subsets (patterns) defined for a list of categorical variables. It computes the mean results over multiple imputations using the previously discussed models. The missing data in either arm can be sampled from the non-missing data from either arm to impute data in each arm. The missing baseline data can also be imputed according to the patterns specified. The primary focus will be to estimate the results when missing data in both the control and experimental arms are imputed from sampling from the non-missing data in the control arm, and when missing data in both the control and experimental arms are imputed from sampling from the non-missing data in the experimental arm, The latter analysis provides an additional

[figure not shown]
Statistical Analysis Plan

Sponsor Name: Seqirus
Sponsor Protocol ID: V130_10

sensitivity assessment appropriate for non-inferiority evaluations. The macro allows for covariates other than baseline (as used in the ANCOVA model specification for the primary analysis).

Seroconversion Binary Outcome Analyses

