Analysis of the seroconversion binary outcome, SCR, is also expected to have missing data. An excellent method of assessing the impact of missing outcomes for a binary outcome is to make a tipping point graph (Yan 2009). A tipping point graph has as its two axes corresponding to the two arms. Each axis ranges from zero to the number of missing values in the corresponding arm. For each possible combination of possible assignments of missing from non-success to success the statistical test is recomputed. In this evaluation we apply sensitivity analysis based upon multiple imputations under the by searching for a tipping point by using "shift" approaches until the inferences change from significance to non-significance, or vice versa. Those analyses meeting statistical criterion are graphed as a point with a colored symbol showing success and the analyses failing statistical criterion are graphed as a point using a symbol of a contrasting color. In general, this graph will then show two regions defined by the colors assigned. The location of the analysis using the default assignment for missing outcome (usually missing is regarded as a non-success) will then be in one of these regions, and the distance this point is from the other region can be assessed as a sensitivity analysis. The statistical test can be based on the usual two group assessment (asymptotic or exact) or with covariates using logistic regression. The following is an example of a tipping point graph.

Statistical Analysis Plan

Sponsor Name: Seqirus
Sponsor Protocol ID: V130_10

REFERENCES

Yan 2009] Yan X, Lee S, Li N. Missing data handling methods in medical device clinical trials, *J Biopharm Stat.* 2009 19(6):1085-98.

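### The planned missing-titer check for GMT fills both arms from one donor arm, so in practice it cannot turn a noninferiority pass into a fail

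*SAP*

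**What the plan says.** SAP 6.5.1.3 decides noninferiority on complete cases in the per-protocol set (PPS). The HAI criterion in SAP 6.5.1.1 is "The upper bound of the two-sided 95% CI on the ratio of the HAI GMTs does not exceed 1.5", and A/H3N2 has the same limit on the MN ratio. SAP 6.5.1.3 then describes an optional, exploratory multiple-imputation analysis on the PPS that "will serve to evaluate the robustness of the non-inferiority conclusions". Appendix C words the same analysis as a firm commitment. It also says that missingness at random cannot be established for follow-up titers, and it announces a pattern-mixture and tipping approach.

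For GMT, Appendix C puts its main weight on two runs. In the first, "missing data in both the control and experimental arms are imputed from sampling from the non-missing data in the control arm". In the second, both arms are filled from observed QIVc titers, and the SAP presents this run as suited to noninferiority. The macro could use other donor combinations, but no penalty on QIVc titers is specified. On pooling, the text says only: "It computes the mean results over multiple imputations using the previously discussed models". The shift search and tipping graph are described under seroconversion (SCR), not under GMT.

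**The concern.** A robustness check for noninferiority should ask how much worse the unobserved QIVc children would have to be before the conclusion fails. Both focal GMT runs instead assume that unobserved children in the two arms respond alike. In a superiority trial that is the cautious assumption. In a noninferiority trial it favours the new vaccine whenever that vaccine looks worse, which is the only situation in which the conclusion is in doubt. At stake is the meaning of a statement in the study report that the GMT conclusions are robust to missing titers. A check that cannot produce an adverse result does not support that statement.

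**Working it through.** **Inputs** (SAP 2.3 unless noted)

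- Evaluable children: 1450 QIVc, 725 QIV. Margin 1.5 for QIV/QIVc. SD of the natural log titer 1.3.
- Alpha: "using a one-sided alpha of 0.025 for each comparison".
- Assumed GMT ratios: "1.49 for the A/H1N1, 1.00 for the A/H3N2 (based on the MN assay) and 0.84 for the B-strains". The protocol synopsis gives their direction as QIVc/QIV, so as QIV/QIVc they are 0.671, 1.00 and 1.190.
- Missing share 10%. This is an assumption borrowed from the drop-out allowance; 2% and 5% were also run.

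**1. The plan's own figure.** SE = 1.3 × √(1/725 + 1/1450) = 0.0591. B-strain power = Φ((ln 1.5 − ln 1.190)/0.0591 − 1.96) = Φ(3.909 − 1.96) = 97.43%, against 97.42% stated. Squaring for two B strains, with the A strains at about 100%, gives 94.93% against 94.90% stated. The inputs and the direction of the ratios are therefore read correctly.

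**2. What one-donor imputation does.** Take simple means. With control donors the QIV mean is unchanged in expectation, and the QIVc mean becomes (1 − p) × QIVc mean + p × QIV mean, where p is the missing share in QIVc. The expected log ratio is then (1 − p) × the observed log ratio. The QIVc-donor run gives the same form, with p the missing share in QIV.

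**3. At p = 10%, with the complete-case SE** (1.96 × 0.0591 = 0.1159):

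| Case | Ratio before → after | Upper limit before → after |
|---|---|---|
| B strains | 1.190 → 1.170 | 1.337 → 1.314 |
| A/H3N2 | 1.000 → 1.000 | 1.123 → 1.123 |
| A/H1N1 | 0.671 → 0.698 | 0.754 → 0.784 |
| Observed ratio 1.36 | 1.36 → 1.32 | 1.527 → 1.48 |
| Observed ratio 1.5 | 1.500 → 1.440 | 1.684 → 1.617 |

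At an observed ratio of 1.36, complete cases fail and the imputed analysis meets the criterion.

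**4. Can a pass become a fail?** The largest log ratio that passes is 0.4055 − 0.1159 = 0.2896. After imputation it is 0.9 × 0.2896 = 0.2606. A fail then needs 1.96 × SE > 0.4055 − 0.2606 = 0.1449, so SE > 0.0739, which is 25% above 0.0591. Under Rubin's rules the simulated SE was ln(1.6149/1.4382)/1.96 = 0.0591, so there is no such increase. If the observed log ratio is zero or negative, the upper limit stays near or below exp(0.1159) = 1.12. In a simulation of 24,000 trials (control donors; true ratios 1.5, 1.36 and 1.19; 5% or 10% missing), no complete-case pass became a fail.

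**5. How often the imputed analysis meets the criterion when the true ratio is 1.5.** At 10% missing, 1612 and 806 children were randomized, with 10 hot-deck imputations, unadjusted means and 3000 trials per run. At 2% and 5% missing, 4000 trials were run with the evaluable numbers held at 1450 and 725. Ranges cover the two donor choices.

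| Missing | Complete cases | One donor, Rubin's rules | One donor, averaged variance only |
|---|---|---|---|
| 2% | 2.7–2.9% | 3.3–3.4% | 3.5% |
| 5% | 2.5–3.0% | 4.4–5.1% | 5.0–5.7% |
| 10% | 2.3–2.4% | 7.6–8.4% | 9.7–10.3% |

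Own-arm donors with Rubin's rules gave 2.9% at 10% missing, where complete cases in the same trials gave 2.8%. The Monte Carlo standard error at 8% is √(0.08 × 0.92/3000) = 0.5 points.

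**6. What a real tipping search would show for B strains at 10% missing.** Solve 0.1744 + 0.1 × δ + 0.1159 = 0.4055, which gives δ = 1.152 in natural logs, or 0.50 in log10. Unobserved children would need a QIV/QIVc ratio of exp(0.1744 + 1.152), about 3.8. That would be a strong and informative result, and neither planned run can deliver it.

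**The case against.** Several points on the other side stand.

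- A reader might infer that the check can only make noninferiority easier. That is not so. Where QIVc is better, as assumed for A/H1N1, the upper limit moves toward the margin (0.754 to 0.784), though no conclusion is at risk there.
- A reader might infer that the plan inflates the trial's type I error. It does not. The analysis is exploratory and complete cases in the PPS decide, so the percentages in step 5 describe how often the check reassures, not how often the trial succeeds wrongly.
- The PPS is drawn from the Full Analysis Set – Immunogenicity, which requires valid assay results before and after vaccination (SAP 4.4 and 4.5). Read literally, almost nothing is left to impute, and at 0% missing nothing changes. The 2% to 10% shares are therefore assumptions. This limits the present harm but is a defect of its own: the check is nearly empty as specified, and repairing only the set would bring the donor bias into play.
- Invalid pooling cannot be asserted. The macro is not shown and the text neither states nor excludes between-imputation variance. The bias remains with Rubin's rules, so the point does not depend on this.
- The criticism does not extend to SCR. The tipping grid there covers every assignment of missing outcomes, including the one least favourable to QIVc.
- The simulation has no covariates or patterns. With patterns, the imputed contrast is only approximately zero.

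**Conclusion.** The concern holds for GMT. Both focal runs in Appendix C give imputed children about zero expected vaccine difference, so where QIVc is worse they pull the ratio away from 1.5, and where it is equal or better the upper limit is far from 1.5 anyway. In practice the check cannot turn a pass into a fail and gives false reassurance about robustness. With 10% of titers missing and a true ratio of 1.5, it would meet the criterion about 8% of the time with Rubin's rules, against about 2.5% for complete cases. At 2% missing the excess is under one percentage point. These sizes rest on the assumed missing share, an SD of 1.3 and unadjusted means. The documents do not support a stronger finding that the primary noninferiority decision is compromised.

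**What to change.** In SAP Appendix C (GMT):

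1. Make the focal analysis own-arm donors within pattern: QIV from QIV, QIVc from QIVc. Appendix C says the macro already lets either arm donate to either arm.
2. Subtract a delta from imputed QIVc log10 titers, starting at 0 and increasing until the upper limit crosses 1.5. Report the tipping delta for each strain. Do not cap it at log10(1.5) = 0.176: at the assumed B-strain ratio and 10% missing, the upper limit there is only exp(0.1744 + 0.1 × 0.4055 + 0.1159) = 1.39, and tipping needs about 0.50.
3. State pooling by Rubin's rules.
4. Run it on a set that keeps otherwise eligible children whose titers are missing, instead of the PPS as defined.
5. Make SAP 6.5.1.3 and Appendix C agree on whether the analysis is optional or committed.
6. Optionally, mark the complete-case result on the SCR tipping graph, since the reference point described there usually counts missing as non-success.

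The cost is SAP wording and some macro work, with no new patients or data. The sensitivity results may look less favourable than under the planned runs.
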